8.1.1 Baseline

Baseline is defined as the last value recorded for any given parameter prior to first study medication injection on Day 1. For qCT and DXA, values recorded from Screening Visit 2 will serve as baseline, regardless of whether the scans took place before or after first study medication injection. Baseline values for Phase B of the study are the same as they were for Phase A.

8.1.2 Analysis of Covariance (ANCOVA)

ANCOVA models will be used to analyze change over time in bone imaging endpoints. All models will be adjusted for baseline. Least squares estimates, two-sided 95% confidence intervals (unadjusted for multiplicity), and effect sizes will be provided.

8.1.3 Mixed-Effects Models for Repeated Measures

A mixed-effects model for repeated measures (MMRM) will be used to analyze change over time in Pain NRS. The model will be estimated assuming a Toeplitz variance-covariance matrix. The Toeplitz structure is a more generalized form of autoregressive-1 (AR1) structure, allowing the data to inform how the correlation between within-subject observations decreases over time instead of implicitly defining a uniform decay structure (Kincaid, 2005).

MMRM presumes that missing data are not caused by something observable within the conduct of the trial (i.e. missing-at-random [MAR]). It is plausible to presume a MAR mechanism as there have been no observed tolerability issues to the administration of study injection during the prior development trials. Additionally, the study injection cannot be removed after it has been administered, eliminating study drug discontinuation as a source of treatment estimate confounding.

8.1.4 Data Handling for Subjects Who Withdrew from Study

If a subject discontinues the study, early termination assessments will be performed according to the protocol. If these assessments occur during a scheduled visit, they will be associated with that visit for the purposes of analysis.

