7.3.6 EARLY TERMINATION VISIT

If possible, the following procedures and assessments should be performed within 14 days of subject premature withdrawal or termination. Subjects should fast for 8 hours prior to this visit.

- Collection of AE and concomitant procedures/therapies/medication data
- Review of medical history
- Vital signs measurements (pulse rate, blood pressure, respiratory rate, and temperature)
- Physical examination, including knee examination of both knees
- Weight measurement
- Venipuncture and collection of samples for clinical laboratory tests and biomarker analysis
- Radiograph – bilateral in weight-bearing fixed flexion position, posterior-anterior (PA) view X-ray
- qCT of both knees
- DXA of the spine and hips

Protocol SM04690-OA-06
Samumed, LLC

AM04V00
21 August 2020

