10.4.2 ANALYSIS OF PHASE A GENERAL SAFETY AND BONE IMAGING ENDPOINTS

The number and percent of subjects experiencing AEs in Phase A will be summarized by seriousness, severity, and relationship for each treatment group.

Change over time in BMD in the target knee as assessed by qCT will be characterized using a mixed-effects model for repeated measures (MMRM) in order to estimate change from baseline with treatment group, week, treatment×week, and baseline as covariates. The model will be evaluated at Week 52. Unadjusted 95% confidence intervals and P values will be reported. The model will be estimated assuming an unstructured variance-covariance matrix, allowing the data to fully inform the correlation between within-subject observations ([Kincaid 2005](#)).

As a sensitivity analysis, analysis of covariance (ANCOVA) will be used to estimate baseline-adjusted BMD in the target knee at Weeks 12, 24, 36, and 52. The ratio of baseline-adjusted BMD between SM04690 and placebo will be presented with a one-sided 95% confidence interval.

Baseline-adjusted ANCOVA will also be used to analyze the within-subject difference in BMD between the target and non-target knee by qCT for SM04690, within-subject difference in BMD between the target and non-target knee by qCT for placebo, and change from baseline in BMD of the spine and hips by DXA for SM04690 subjects versus placebo. The models will be adjusted for baseline and evaluated at Weeks 12, 24, 36, and 52 for qCT and Weeks 24 and 52 for DXA. Unadjusted 95% confidence intervals and P values will be reported.

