8 GENERAL ISSUES FOR STATISTICAL ANALYSIS

8.1 General Statistical Methodology

For continuous variables, the outcome measure at each visit, as well as the absolute change (outcome at visit – outcome at baseline), will be summarized within each treatment group using descriptive statistics (number of subjects, mean, standard deviation (SD), median, minimum, and maximum). The number of evaluable subjects in any analysis set may vary by endpoint/timepoint based on missing data. Categorical variables will be summarized with frequency tables.

All subject-level listings will be comprehensive and include subjects enrolled in both Phase A and Phase B. Data collected from unscheduled visits will not be included in summary tables but will be included in subject-level listings as appropriate.

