11 BONE IMAGING ANALYSIS

Whereas Phase A analysis (defined prior to unblinding) was the primary analysis for this study, data collected during Phase B complements the primary analysis by offering insight into safety after more than one year of treatment. Bone imaging analysis will be performed on the SAS.

A statistical description of target knee, non-target knee, spine, and hip BMD at baseline will be provided along with absolute and percent changes from baseline at each subsequent timepoint. Statistical descriptions of knee BMD for subgroups such as KL grade, sex, and age group may be provided.

Difference between target knee and non-target knee BMD will be summarized at baseline along with absolute changes from baseline at each subsequent timepoint. Spine and Hip BMD T-scores will be summarized at baseline only for subjects enrolled in Phase B.

Baseline-adjusted ANCOVA as described in [Section 8.1.2](#) will be used to analyze the change from baseline in BMD in the target knee and evaluated at Weeks 12, 24, 36, 52 (EOSa), 64, 76, 88, and 104 (EOSb).

Baseline-adjusted ANCOVA will also be used to analyze the within-subject difference in BMD between the target and non-target knee by qCT for SM04690, within-subject difference in BMD between the target and non-target knee by qCT for placebo, and change from baseline in BMD of the spine and hips by DXA for SM04690 subjects versus placebo. The models will be evaluated at Weeks 12, 24, 36, 52 (EOSa), 64, 76, 88, and 104 (EOSb) for qCT and Weeks 24, 52, 76, and 104 (EOSb) for DXA.

Knee BMD analysis will include all compartments and volumes of interest. Spine BMD analysis will include the adjusted total region of interest; hip BMD analysis will include both total hip and femoral neck regions of interest.

Subject-level listings will be provided.

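### The Phase B SAP replaces the protocol's MMRM for target-knee BMD with ANCOVA without declaring it, so the Week 64 to 104 results are complete-case; off-schedule early-termination scans also have no analysis slot

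*SAP*

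**What the plan says.** **Model in the Phase B SAP.** Section 8.1.2: "ANCOVA models will be used to analyze change over time in bone imaging endpoints". Section 11 gives the purpose and the weeks of the baseline-adjusted ANCOVA: "analyze the change from baseline in BMD in the target knee and evaluated at Weeks 12, 24, 36, 52 (EOSa), 64, 76, 88, and 104". It also names the population: "Bone imaging analysis will be performed on the SAS". Under SAP 7.6 that set is everyone with at least one injection, whether or not they entered Phase B. Section 8.1.3 keeps MMRM for Pain NRS only.

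**Model in the protocol.** Section 10.4.2, for Phase A: "Change over time in BMD in the target knee as assessed by qCT will be characterized using a mixed-effects model for repeated measures (MMRM"). The covariates are treatment, week, their interaction and baseline, with an unstructured covariance. ANCOVA at individual weeks is labelled a sensitivity analysis. Protocol 10.4.4 and SAP 5.2 both say that Phase B endpoints will be analysed much as the Phase A endpoints were. SAP Section 15 lists one change only, the reference point for biomarkers.

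**Early-termination (ET) scans.** Protocol 7.3.6: "If possible, the following procedures and assessments should be performed within 14 days of subject premature withdrawal or termination". The list includes qCT of both knees and DXA. SAP 8.1.4: "If these assessments occur during a scheduled visit, they will be associated with that visit for the purposes of analysis". No sentence covers an ET scan on any other day. SAP Appendix 1 has windows for WOMAC, Patient Global Assessment and Pain NRS, and none for imaging. SAP 8.1 adds: "Data collected from unscheduled visits will not be included in summary tables but will be included in subject-level listings as appropriate". SAP 8.1.5 rules out imputation for efficacy and does not mention bone imaging.

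**The concern.** Safety is the primary objective, and the sample size rests on knee BMD. Repeated qCT in the same subjects suits a longitudinal model, because a leaver's earlier scans then inform the later-week estimates under a missing-at-random assumption. ANCOVA at a single week cannot do that. A subject with scans at Weeks 12 to 52 and none afterwards adds nothing at Weeks 64, 76, 88 or 104. This includes SAS subjects who never entered Phase B. The population label says all treated subjects, but the later estimates describe those still being scanned.

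The ET gap adds to this. A leaver's last BMD measurement may have been taken and still have no stated place in the analysis. SAP 4.3 says the Sponsor was unblinded after the Phase A analysis. Without a written rule, the placement of ET scans would be settled with treatment codes known.

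**Working it through.** **1. The plan's own figure.** SAP Section 6 gives 81.6% power for a BMD ratio of 0.93 against a bound of 0.80, with CV 0.30, 50 per group and Type 1 error 0.05 (one-sided).
- Difference: ln(0.93/0.80) = 0.1506
- Log-scale SD: sqrt(ln(1 + 0.30²)) = 0.2936
- SE: 0.2936 × sqrt(2/50) = 0.0587
- Noncentrality: 0.1506/0.0587 = 2.56

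The noncentral t with 98 df gives 81.65%. The figure reproduces and is not in dispute.

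**2. What complete-case analysis costs in precision.** The documents give no dropout rate, so the missing fraction m is an assumption, shown as a range and taken as equal in both arms. The SE factor is 1/sqrt(1 − m). Power is step 1 repeated with 50(1 − m) per group.

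| Missing at the week (assumed) | Scanned per group | SE factor | Power |
|---|---|---|---|
| 5% | 47.5 | 1.026 | 79.9% |
| 10% | 45 | 1.054 | 77.9% |
| 20% | 40 | 1.118 | 73.5% |
| 30% | 35 | 1.195 | 68.4% |

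This is the cost of the missing scans. MMRM would recover part of it, depending on the correlation between visits, which the documents do not give.

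**3. How much of the calendar the visit windows cover.** From Protocol 7.3.3 to 7.3.5 and the schedule in 7.3.7, over Days 2 to 728 (727 days):
- qCT: Week 12, Days 82–88 (7 days); Week 24, 169–172 (4); Week 36, 250–260 (11); Week 52, 362–372 (11); Weeks 64, 76 and 88 (8 each). Total 57. 57/727 = 7.8%.
- DXA: Weeks 24, 52 and 76 give 4 + 11 + 8 = 23. 23/727 = 3.2%.

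Protocol 7.3.3 gives the Week 24 window as plus or minus 3 days, while 7.3.7 gives plus 3; these should be reconciled. The wider reading makes the qCT total 60 days (8.3%).

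If ET visits fell evenly over these days (assumption), about 92% of ET qCT scans and 97% of ET DXA scans would match no window. With an assumed window of plus or minus 7 days at every qCT visit, 615 of 727 days (85%) still lie outside. For 5, 10, 20 or 30 leavers among 100 subjects, 670/727 of them is about 5, 9, 18 or 28 unplaced ET qCT scans. These are upper-end counts, because ET visits are done only if possible. Exits that cluster near visits would lower them.

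An ET DXA done during a Week 64 or 88 visit also has no modelled week. Section 11 evaluates DXA only at Weeks 24, 52, 76 and 104.

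**4. What placing ET scans could return to Week 104.** With nearest-week assignment, an ET qCT reaches Week 104 only from the midpoint of Days 617 and 729, which is Day 673. If exits are even over the 364 days of Phase B (assumption), that is 56/364 = 15% of leavers. For DXA the midpoint of Days 533 and 729 is Day 631, so 98/364 = 27%. Suppose 20% are missing. Mapping then returns 0.20 × 0.154 = 3.1 points, and the SE factor falls only from 1.118 to 1/sqrt(0.831) = 1.097. Placing ET scans is therefore the smaller remedy.

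**The case against.** The strongest reply has four parts.

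- *The protocol's MMRM is the Phase A model, evaluated at Week 52, and Phase B has its own SAP.* True, and the Phase B wording leaves latitude. But making the named sensitivity method the only method is a change of main model, and a section for listing changes exists without mentioning it. The point is limited to target-knee qCT: Protocol 10.4.2 already assigned ANCOVA to DXA and to the target versus non-target difference.
- *Phase B is complementary and no formal test is planned* (SAP Section 11, Protocol 10.2). This limits the weight of the point. It does not make a complete-case estimate an all-treated one.
- *Nothing says ET scans are excluded.* Correct. A reader might infer exclusion from "Data collected from unscheduled visits will not be included in summary tables", but ET is a named protocol visit, that sentence concerns summary tables, and Section 11 describes BMD at each later time point. The SAP is silent on off-schedule ET scans.
- *Subjects stopped for safety stay under observation.* Protocol 5.5.2 and 6.1.9 keep subjects withdrawn from study medication for safety, or judged unsuitable for injection, on all planned visits. A reader might infer that leavers are those losing most bone. The documents contain no such data, and these provisions weaken the inference. Equal dropout and equal loss in both arms would leave the contrast between arms unbiased.

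**Conclusion.** The point holds in two parts. The main one is an undeclared move from MMRM to ANCOVA for target-knee qCT BMD, which makes the Week 64 to 104 results complete-case while they carry the SAS label. This assumes that ANCOVA evaluated at a week is fitted to the subjects scanned at that week, which is its ordinary meaning. The second is a gap: off-schedule ET qCT and DXA scans have no analysis slot. On protocol windows and evenly spread exits, that is about 92% and 97% of such scans.

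Limits:
- A leaver's earlier scheduled scans still count at their own weeks.
- A subject who completes Phase A and declines Phase B has a scheduled Week 52 scan, so is affected by the model choice rather than by the ET gap.
- A reader might conclude that leaving out ET scans is what makes the Week 104 estimate a stayers-only one. It is not: under step 4's assumptions, mapping would return only about 15% of Phase B leavers for qCT.
- The size and direction of any bias between arms cannot be stated.
- The Phase A SAP is not among the documents, so the Week 52 primary analysis is not judged.
- Medial joint space width is only described in Phase B (SAP Section 12) and is not part of this point.

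**What to change.** **Main change, SAP Section 11.** Make an MMRM on the SAS, with treatment, week, treatment-by-week and baseline, the main model for target-knee qCT BMD through Week 104. Keep visit-wise ANCOVA as the sensitivity analysis. If ANCOVA is retained as the main model instead, record and justify this in Section 15.

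**Secondary change, SAP 8.1.4 and Appendix 1.**
- Add qCT and DXA analysis windows with a stated maximum distance. Uncapped nearest-week assignment could place a scan up to 56 days (qCT) or 98 days (DXA) from its nominal day.
- Give a scheduled scan precedence over an ET scan in the same window.
- Do not carry an ET scan taken after an injection back into a pre-injection visit slot. Uncapped nearest-week assignment would put a Day 400 scan into Week 52 (midpoint of Days 365 and 449 is Day 407), although Week 52 scans are scheduled before that visit's injection.
- Summarise last on-study BMD by arm for ET scans outside every window.

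**Cost.** One extra model and one derivation rule, with no new data. An unstructured covariance over eight visits has 8 × 9/2 = 36 parameters in about 100 subjects and may not converge, so name a fallback structure in advance; the SAP already uses Toeplitz for Pain NRS. Some ET scans will sit off their nominal day. No sample-size or power statement changes.

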8.1.5 Imputation of Missing Data

No imputation will be performed for Phase B efficacy analysis.

8.2 General Safety Assessments

8.2.1 Adverse Events

An AE is any unfavorable and unintended sign, symptom, or disease temporally associated with the use of an IP or other protocol-imposed intervention, regardless of attribution. Signs and symptoms of exacerbation or worsening of target knee OA were captured in the context of efficacy assessments. Anticipated fluctuations or anticipated deterioration (in the opinion of the Investigator) of the underlying disease (target knee OA) were not considered as AEs.

Severity was assessed utilizing the CDISC AESEV, which classifies AEs as mild, moderate, or severe. For analysis, relationship will be dichotomized into Unrelated (combining Not Related and Unlikely Related) and Related (combining Possibly Related and Probably Related).

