7. STUDY PROCEDURES AND SCHEDULE

7.1 STUDY PROCEDURES/EVALUATIONS

7.1.1 STUDY SPECIFIC PROCEDURES

Collection of Adverse Events Data

Data regarding AEs will be collected in this study. AEs are events that occur during the course of the study that are not present prior to Day 1 study medication injection, or, if present at the time of study medication injection, have worsened in severity during the course of the study. AEs will be assessed at each study visit from the time of study medication injection on study visit Day 1 through the subject's last study visit.

Each subject will be observed and queried by the Investigator or the Investigator's designee at each study visit for any continuing AEs or new AEs since the previous visit. The subject may be asked to return to the site for an unscheduled visit if an AE occurs between study visits, and if, in the opinion of the Investigator, the AE requires a study visit for full evaluation. Any AE reported by the subject or noted by the Investigator or the Investigator's designee will be recorded within the eCRF. The following information will be recorded for each AE: description of the event, date of onset and resolution, etiology, and severity as assessed by the Investigator according to the Clinical Data Interchange Standards Consortium (CDISC) Severity/Intensity Scale for Adverse Events (AESEV) ([Table 1](#)), causal relationship to study medication, outcome, and any treatment given.

In this protocol, signs and symptoms of exacerbation or worsening of target knee OA will be captured in the context of efficacy assessments and recorded on specific pages of the eCRF.

Anticipated fluctuations or anticipated deterioration (in the opinion of the Investigator) of the underlying disease (target knee OA) will not be considered as AEs nor captured on the AE page of the eCRF.

Whenever possible, it is preferable to record a diagnosis as the AE term rather than a series of symptoms relating to a diagnosis. Fluctuations of pre-existing conditions, including the disease under study, that do not represent a clinically significant exacerbation or worsening, need not be considered AEs.

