AEs that are ongoing at a subject's last visit will be followed for 30 days after administration of the last dose of study medication or until resolution, whichever comes first. Resolution is defined as the return to baseline status or stabilization of the condition. SAEs that are ongoing at a subject's last visit will be followed until resolution.

Medical History

A medical history will be obtained at Screening Visit 1 and Day 1 with a follow-up at Weeks 52 (EOSa) and 104 (EOSb) or ET to capture End Dates of any ongoing medical history collected at screening. Medical history at Screening Visit 1 will include demographic data (e.g., age, race, ethnicity) and usage of assistive devices. In addition, medical information will also be recorded, including all (1) medical conditions and disease states that require current or ongoing therapy and (2) other medical conditions and disease states that, in the opinion of the Investigator, are relevant to the subject's study participation. Examples of medical conditions and disease states that should be considered relevant to the subject's study participation include history of current disease, medical history that confirms the eligibility criteria of the subject, and asymptomatic medical history that could become symptomatic while on the study.

Physical Examination

A general physical examination will be conducted at all visits except Screening Visit 2. Results of the physical examination will be noted in the source documents. Any clinically significant finding noted prior to study medication injection should be recorded as medical history. If it is found after study medication injection, it should be reported as an AE.

Knee Examination

A knee examination of both knees will be conducted at all visits except Screening Visit 2. Results of the knee examination will be noted in the source documents. Any clinically significant finding noted prior to study medication injection should be recorded as medical history. If it is found after study medication injection, it should be reported as an AE.

Presence of unilateral or bilateral knee OA will be recorded in the eCRF at Screening Visit 1. If the subject has OA in both knees, the site is to establish the target knee as the knee with greater pain at Screening Visit 1 based on the subject's evaluation and the Investigator's clinical judgment.

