3 STUDY OBJECTIVES AND ENDPOINTS

3.1 Study Objective

3.1.1 Primary Objective

The primary objective of this study was to evaluate the safety and tolerability of SM04690 Injectable Suspension administered every 6 months through 52 weeks for the treatment of knee osteoarthritis (OA).

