12 EFFICACY ANALYSIS

A statistical description of Pain NRS at baseline will be provided along with absolute changes from baseline at each subsequent timepoint for subjects in the FASB and PPASB. Statistical descriptions of WOMAC Pain, WOMAC Function, Patient Global Assessment, and mJSW at baseline will also be provided along with absolute changes from baseline at each subsequent timepoint for subjects in the FASB only.

Changes in the target knee from baseline in Pain NRS will be characterized using MMRM for subjects in the FASB and PPASB; the models will be evaluated through Week 104 (EOSb). All models will use treatment group, week, treatment×week interaction, and baseline values as covariates. Unadjusted 95% confidence intervals and P values will be reported.

If a subject submitted data related to their non-target knee due to an electronic device error, this data will not be analyzed.

Subject-level listings will be provided.

Since Phase A analysis (defined prior to unblinding) was the primary analysis for this study, there will be no estimands provided for Phase B.

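### Target-knee worsening judged anticipated is kept out of the AE tables, and the Phase B SAP plans no count of subjects who worsen after an injection

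*SAP*

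**What the plan says.** SAP 3.1.1 sets the aim: "The primary objective of this study was to evaluate the safety and tolerability of SM04690 Injectable Suspension".

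Three rules govern how a worse injected knee is recorded.

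- **Routing.** SAP 8.2.1 states: "Signs and symptoms of exacerbation or worsening of target knee OA were captured in the context of efficacy assessments". Protocol 7.1.1 has the same rule and names dedicated eCRF pages for the record; Protocol 8.1.1 adds the electronic diary. This sentence covers all worsening.
- **Exclusion.** The same SAP section continues: "Anticipated fluctuations or anticipated deterioration (in the opinion of the Investigator) of the underlying disease (target knee OA) were not considered as AEs". Protocol 7.1.1 says such changes "will not be considered as AEs nor captured on the AE page of the eCRF". This covers only anticipated change. Protocol 7.1.1 also exempts fluctuations, including those of the disease under study, "that do not represent a clinically significant exacerbation or worsening, need not be considered AEs".
- **Knee examination.** For a clinically significant finding, Protocol 7.1.1 says: "If it is found after study medication injection, it should be reported as an AE".

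On outputs, SAP 10.1 plans a table of target-knee-related AEs and SAEs by preferred term, for the whole study and for Phase B, with AE listings. SAP 12 says: "A statistical description of Pain NRS at baseline will be provided along with absolute changes from baseline at each subsequent timepoint", for the FASB and PPASB. It adds an MMRM for Pain NRS and subject-level listings. SAP 8.1 specifies mean, SD, median, minimum and maximum. SAP 8.1.1 keeps the Phase A baseline for Phase B. No output counts worsened subjects or summarises the eCRF worsening pages, and Protocol 8.4.4 defines no events of special interest.

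**The concern.** A local flare after injection is the most direct tolerability question for this product. Whether a flare reaches the AE tables depends on whether the Investigator calls it anticipated. If so, it passes to the efficacy data, where subjects who worsen are summarised together with subjects who improve and no table says how many worsened. Some subjects in one arm could flare after injections while the AE table looks clean and the Pain NRS summaries look ordinary.

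**Working it through.** **The plan's own figure.** The plan gives no figure on this point. Its one design figure, 81.6% power for a BMD ratio, reproduces: log-scale SD √ln(1 + 0.30²) = 0.294, distance ln(0.93/0.80) = 0.151, 50 per arm, one-sided 5%, noncentral t gives 81.6%. Only the 50 per arm is used below.

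**Reference point.** Every change in SAP 12 is from the Day 1 baseline. Take a subject who enters at 6 (entry range 4 to 8), is at 3 in the week before the Week 52 injection, and returns to 6 afterwards. Change from baseline is 6 − 6 = 0. Change from the pre-injection week is 6 − 3 = +3. The mean, median, minimum and maximum of change from baseline do not reveal this.

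**Timing of visits (Protocol 7.3).** The Day 1 injection is followed by a visit at Day 29. After the other three, the next scheduled visit is nominally 84 days later:

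- Week 24 to 36: 253 − 169 = 84
- Week 52 to 64: 449 − 365 = 84
- Week 76 to 88: 617 − 533 = 84

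Unscheduled visits for AEs are possible but discretionary. Until the next monthly questionnaire, the diary is the only scheduled record of the target knee.

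**Population.** Whole-study AE tables use the SAS. The efficacy summaries use the FASB or PPASB, so a subject who flared in Phase A and was not injected in Phase B is absent from them.

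**How far a mean moves.** Flare size, share and SD here are assumptions; the documents give none. A flare is measured against the subject's expected course. It cannot be 4 points above baseline for anyone entering above 6.

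Standard error of an arm difference = 2.2 × √(2/50) = 0.44. Mean shift = share × size. Power is for a two-sided 5% test.

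| Share of active arm | Size | Mean shift | Power |
|---|---|---|---|
| 10% | 4 | 0.4 | 15% |
| 10% | 3 | 0.3 | 10% |
| 5% | 4 | 0.2 | 7% |

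Allowing for the extra variance from flaring subjects gives 14%, 10% and 7%.

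Short flares are diluted further, because Pain NRS is a weekly average. With all 7 days scored, +3 points for 1 to 3 days raises the subject's weekly value by 3 × 1/7 = 0.43 to 3 × 3/7 = 1.29. If 5% to 20% of an arm flare this way, the arm mean moves by 0.02 to 0.26. With an assumed SD of 1.5 to 2.5 the standard error is 0.30 to 0.50.

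**Would a count do better as a test?** Ten percent extra is about 5 of 50. Two-sided Fisher test, 50 per arm:

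| Placebo subjects crossing the threshold | Power for 10% extra |
|---|---|
| 0% | 38% (5/50 v 0/50 gives p = 0.056) |
| 10% | 16% to 20% |
| 20% | 11% to 16% |

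The lower value in each range lets the added flares fall partly on subjects who would cross anyway. A count therefore shows who worsened, but is not a powerful test. Phase B numbers can only be the same or smaller.

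**The case against.** A reader might infer that flares are tabulated nowhere. The documents do not support that. The exclusion is confined to anticipated change in the underlying disease, and a reaction to the injection is not obviously that. The AE definition in Protocol 8.1.1 covers anything temporally associated with the product or a protocol procedure, Protocol 8.2.2 grades relatedness to the injection, and SAP 10.1 tabulates target-knee AEs.

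A reader might also infer that only group means are planned. That is wrong too: the maximum change shows the worst subject each week, and listings show each subject. The clash with the knee-examination rule is smaller than it first appears, because the exemption for fluctuations stops at clinically significant worsening. Finally, the Day 1 and Week 24 injections belong to Phase A, whose SAP was not supplied. Protocol 10.4.3 does plan Phase A models of change from Week 24.

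All of this stands and sets the limits of the point. What remains is that anticipated flares leave the AE tables by rule, and neither a maximum nor a listing is a count by arm. The Phase A models from Week 24 compare means, and SAP 12 has no injection-referenced analysis for Phase B, although SAP 3.2.7 lists durability endpoints between injections.

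**Conclusion.** The point holds for the supplied plan and in limited form. Target-knee worsening that the Investigator judges anticipated is excluded from the AE tables, and the Phase B SAP has no by-arm count of subjects who worsened after an injection. Its baseline-referenced summaries can miss a flare relative to the pre-injection state. Under the stated assumptions, a flare in 5% to 10% of active subjects would be detected in the means only 7% to 15% of the time.

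Nothing in the documents indicates that flares occurred or that the product causes them, and nothing is established about the Phase A SAP. This is a cheap improvement to the tolerability reporting. It does not invalidate the planned AE analysis.

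**What to change.** 1. **Add one descriptive table to SAP 10**, by arm and for each injection, in SAS subjects who received it: number and percent whose Pain NRS in any of the 4 weeks afterwards exceeds the week before that injection. Show several thresholds fixed before lock, for example 1, 2 and 3 points. Anchor the weeks on the actual injection date, since Protocol 6.1.5 allows the later injections to be delayed by up to two weeks while SAP 8.4.1 counts weeks from Day 1. State the number evaluable.
2. **Summarise by arm the eCRF pages** on which worsening is recorded.
3. **Reconcile the wording**: the routing sentence (all worsening), the exclusion sentence (anticipated change only) and the knee-examination rule, so that the reader knows which events the AE tables contain.

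A count of subjects with WOMAC worse than baseline at Weeks 52 and 104 would not serve. It has no threshold, and those visits fall 28 weeks after the preceding injection (52 − 24 and 104 − 76).

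The cost is one table and one summary from data already collected. There are three downsides. The thresholds are a choice. They would be set after the sponsor was unblinded to Phase A (SAP 4.3), so the table must be labelled descriptive. With 50 per arm it has little power as a formal comparison. Weekly averages will still miss very short flares.
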